1.0 Background

With the production of high quality imaging systems and improved surgical instruments, video-assisted thoroscopic surgery (VATS) has increased in popularity. When compared to an open technique VATS has been shown to decrease opioid requirements, decrease length of stay and lead to decreased shoulder dysfunction. VATS surgery has also been shown to decrease time until patients resume their normal activity. Despite these statistics, pain following VATS can be severe and long lasting. In addition to non-steroidal anti-inflammatory drugs and systemic opioids, paravertebral nerve blockade and epidural with local anesthetics have emerged as viable adjuncts for control of post-operative pain. Chronic pain after thoracotomy has been studied extensively, and VATS has also been associated with similar rates of chronic pain when compared with open techniques.

Currently, there is no standard of care for post-operative pain control for these patients. The standard of care varies largely, depending on the anesthesiologist or the surgeon. Some anesthesiologists prefer thoracic epidural while others prefer paravertebral block. Each of these pain control techniques have been studied individually and have been shown to provide benefits. Komatsu et al showed that adequate post-thoracotomy pain control was accomplished by continuous paravertebral blockage, while Yoshioka et al showed that epidural analgesia provide effective pain control after surgery. Our study aim is to compare three different methods of pain control that have been proven to show benefit in VATS and compare the efficacy versus the side effects of each techniques. We also aim to look at the effect of these different regional techniques on pain 6 months after surgery.

As mentioned above, several regional techniques have been described for post thoracotomy pain and adapted to VATS. The three most common techniques are:

- 1) paravertebral block using anatomical or ultra-sound guidance
- 2) visual placement of extrapleural paravertebral catheter by thoracic surgeons
- 3) thoracic epidurals

Previous studies have demonstrated that both thoracic epidurals and paravertebral blocks provide adequate analgesia for VATS. Thoracic epidurals provide excellent pain relief but are associated with hypotension and more nausea/vomiting. Paravertebral catheters have the advantage of having a lower side effect profile than thoracic epidurals. Paravertebral blocks have also been shown to improve respiratory function after surgery. Single shot paravertebral blocks have been described as providing adequate post-VATS pain control, despite a shorter duration of action compared to catheter. In order to evaluate the effectiveness and the side effects of the different pain modalities for post-VATS pain control, we will compare these three different methods of pain blocks:

- 1)single shot paravertebral block
- 2)paravertebral catheters
- 3)thoracic epidural

Rationale and Specific Aims

All of the pain control modalities allow for titration and continuous infusion of local anesthetic to achieve adequate pain control for the duration that the catheter remains in place, except for the single shot paravertebral block. The specific aim of the study is to compare the difference between the three pain blocks in achieving the following:

1. Improved postoperative pain scores
2. Decreased opioid requirements
3. Improved patient satisfaction scores
4. Decreased opioid side effects (Nausea, sedation, ileus, urinary retention, respiratory depression)

The primary endpoint of this study will be VAS pain score. The VAS scores will be taken with both rest and movement.

The secondary endpoint includes intravenous opioid consumption and opioid side effects (nausea, sedation, ileus, urinary retention, respiratory depression). The IV and PO opioid doses will be quantified at 1, 24, 48, and 72 hours. We will also measure postoperative nausea and sedation scores at 1, 24, 48, and 72 hours. We will also measure time to first bowel movement, incidence of urinary retention, incidence of respiratory depression, and time to discharge. If subjects are discharged prior to completing the 72-hour endpoints, efforts will be made to contact them and obtain data points. If unable to be reached, or unable to collect data, we will not consider these deviations since it will not change the integrity of the study data.

All patients will receive a phone survey 6 months after surgery to assess for pain and quality of life. If the 6 month questionnaire is unable to be completed, we will not consider this a deviation since it will not affect the integrity of the study data. However, every attempt will be made to complete a follow up questionnaire.

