3.0 Enrollment/Randomization

All VATS cases scheduled by thoracic surgeons at IU Health University Hospital will be identified. The subjects will be contacted face-to-face prior to surgery. They will be informed about the study and all questions will be answered. The potential subjects will be given a copy of the informed consent form and authorization form. The subjects will then be contacted face-to-face in POCU on the day of surgery and if participation is agreed, written consent will be taken.

A total of 120 subjects will be randomized by a computer program into three groups (40 per group):

1. US- Guided Paravertebral Catheter (PVB-A)- The Alaris pump will deliver 0.2% Ropivacaine at a rate of 10 ml/hr
2. Single Shot Paravertebral Block- placed by ultrasound using 0.2% Ropivacaine bolus.
3. Thoracic Epidural- The Alaris pump will deliver an epidural mixture of 0.125% bupiv/hydromorphone

Randomization will be stratified by prior opioid experience (opioid naïve or opioid tolerant). Separate randomization lists will be used for the two strata.

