4.0 Study Procedures

All the thoracic epidurals and ultrasound-guided paravertebral blocks will be placed preoperatively. All procedures will be done using sterile technique with masks, hats, and sterile gloves. All procedures will be placed under the supervision of the attending anesthesiologist on the acute pain service or the attending anesthesiologist in the VATS room.

Thoracic epidurals will be placed using the Arrow thoracic epidural kit. Fentanyl and midazolam will be given prior to epidural placement. The epidural will be placed at the appropriate level to cover the entry site for the VATS procedure. Placement will be determined by anatomical landmarks. The epidural needle will be advanced toward the epidural space utilizing a Paramedian approach and loss-of-resistance technique. A sterile catheter will then be secured in place and the epidural infusion will be started at the end of the case.

Ultrasound guided paravertebral catheter and single shot paravertebral block will be accomplished using an ultrasound transducer at the thoracic level. This will be done using an in-plane or out-of-plane approach, at the discretion of the anesthesia staff performing the procedure. Then a needle will be inserted the needle into the paravertebral space and local anesthetic injected. Then a catheter will be placed within the injectate and secured in place in the case of the paravertebral catheter. The 0.2% Ropivacaine will be delivered by OnQ pump.

General anesthesia will be induced and the patient will be placed in the lateral position for the VATS procedure. The patients will be intubated with dual lumen endotracheal tubes and placed on one-lung ventilation for the procedure.

All patients will receive intravenous patient-controlled analgesia (PCA hydromorphone) post-operatively for breakthrough pain. Usual standard of care for pain control following a VATS procedure include scheduling PO acetaminophen and PO oxycodone PRN on POD 1 once patients tolerate diet.

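### The opioid endpoint lists only IV and oral doses, although the epidural arm alone receives hydromorphone in its block infusion, so lower IV+PO use with the epidural cannot be read as a lower total opioid requirement

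*Combined protocol and SAP*

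**What the plan says.** **Opioid endpoint.** Section 1.0 (Rationale and Specific Aims) gives "Decreased opioid requirements" as the second of four aims. It then names opioid consumption by the intravenous route as a secondary endpoint and adds: "The IV and PO opioid doses will be quantified at 1, 24, 48, and 72 hours". No other place in the document lists routes. Section 4.0 (recording) and Section 7.0 (outcomes and analysis) refer to opioid usage at the same four times without a route. Section 7.0 analyses it by repeated measures ANOVA.

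**Assigned infusions.** Section 3.0 describes the arms as follows:
- Thoracic epidural: "The Alaris pump will deliver an epidural mixture of 0.125% bupiv/hydromorphone".
- Paravertebral catheter: "The Alaris pump will deliver 0.2% Ropivacaine at a rate of 10 ml/hr".
- Single-shot block: "placed by ultrasound using 0.2% Ropivacaine bolus".

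Section 4.0 gives every patient a postoperative hydromorphone PCA for breakthrough pain, and describes oral oxycodone as needed from the first postoperative day as usual care.

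**Side effects.** Section 1.0 says the study will weigh the efficacy of each technique against its side effects, and it names hypotension as a drawback of epidurals. The outcome lists in Sections 1.0, 4.0 and 7.0 do not include hypotension. Section 5.0 says that normally expected risks of the three procedures will not be treated as adverse events.

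**The concern.** The same drug is counted when a patient takes it by PCA and falls outside the route list when it runs through the epidural. Fewer IV and oral doses in the epidural arm could mean better analgesia, or opioid moved to a route that nobody counts. The plan as written cannot separate the two, yet the aim speaks of requirements.

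The part of Section 1.0 that defines the endpoint does not mention that one infusion carries an opioid: "All of the pain control modalities allow for titration and continuous infusion of local anesthetic" is its description, with the single-shot block as the only exception.

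The fourth aim concerns opioid side effects, which can reflect opioid from any route. In the epidural arm, aims 2 and 4 would then rest on different exposures. With the definition left open, it could also be settled after the data are seen.

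The balance of efficacy against side effects would in addition lack one harm that the rationale itself names.

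**Working it through.** **1. Plan's own figure.** There is none to reproduce. The sample-size statement in Section 7.0 concerns VAS only, and no assumption is given for opioid use.

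**2. Routes by arm** (Sections 1.0, 3.0 and 4.0).

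| Arm | n | Opioid by PCA or mouth (in the IV/PO list) | Opioid in the block infusion (outside the list) |
|---|---|---|---|
| Thoracic epidural | 40 | yes | hydromorphone |
| Paravertebral catheter | 40 | yes | none |
| Single shot | 40 | yes | none |

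Three arms give 3 × 2 / 2 = 3 pairs. Two pairs contain the epidural arm and one does not. The patients assigned an unlisted route are 40 of 120, or one third.

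**3. Direction.** Let S_p and S_e be mean IV+PO opioid, in one common unit, in a paravertebral arm and in the epidural arm. Let H ≥ 0 be mean epidural hydromorphone in mg, and k ≥ 0 the factor that converts it to the common unit. Then

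total difference = S_p − (S_e + kH) = (S_p − S_e) − kH.

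- If S_e < S_p, IV+PO favours the epidural. The total difference shrinks as k grows and changes sign at k = (S_p − S_e)/H, so the IV+PO result does not settle the question.
- If S_e ≥ S_p, the total difference is zero or negative for every k ≥ 0. A paravertebral advantage keeps its direction and can only widen.
- Catheter versus single shot has no kH term.

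**4. Size.** H = concentration × rate × hours. Section 3.0 gives neither the hydromorphone concentration nor the epidural rate, and no conversion factor appears anywhere. The bias therefore has a sign but no computable magnitude.

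**5. Open details that bear on the count.**
- *Unit.* IV hydromorphone and oral oxycodone are analysed as one quantity, with no equivalent unit stated.
- *Clock.* Section 4.0 counts from the block, and "All the thoracic epidurals and ultrasound-guided paravertebral blocks will be placed preoperatively". The epidural infusion starts at the end of surgery, so the 1 h count may close before it begins if the case is still running. The omission thus matters mainly at 24, 48 and 72 h. Read literally, any intraoperative opioid falls inside the count, while fentanyl before the epidural ("Fentanyl and midazolam will be given prior to epidural placement") falls outside it.

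**6. Hypotension: precision at 40 per arm.** By the normal approximation the half-width is largest at a rate of 0.5.
- One arm: 1.96 × √(0.25/40) = 0.155, or 15.5 points.
- Difference between two arms: 1.96 × √(0.25/40 + 0.25/40) = 0.219, or 21.9 points.
- No events in 40: the exact two-sided upper 95% limit is 1 − 0.025^(1/40) = 0.088, or 8.8%.

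These widths support description, not a powered comparison.

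**The case against.** The strongest defence is that the endpoint was always meant to be rescue opioid. Section 1.0 names the intravenous route, every arm has a PCA for breakthrough pain, and the epidural mixture is the assigned treatment, not a response to pain. On that reading IV+PO is a valid measure. This much stands. But the plan never uses such a label, it calls the aim a requirement, and it nowhere says that the epidural opioid was set aside on purpose.

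A second defence is that Sections 4.0 and 7.0 name no route, so the epidural drug may be included. This also stands in part. A reader might infer that the plan expressly excludes epidural hydromorphone; the text only leaves it undefined. If it is included, Section 1.0 must be brought into line and a rule for combining routes is needed.

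A reader might also infer that neither epidural comparison can support any statement about opioid requirement. That goes too far: a paravertebral advantage on IV+PO would stand (working, step 3).

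The unit and clock points are mainly missing detail. The block clock also governs the VAS, nausea and sedation scores, so it is not a defect of the opioid endpoint alone.

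On hypotension, aim 4 is limited to opioid side effects and the outcome list matches it. Nausea, part of the other epidural drawback named with hypotension, is scored. The general promise to compare side effects does not commit the trial to every harm. What remains is that a harm singled out in the rationale is not an outcome, and Section 5.0 makes it unlikely that adverse event reporting will supply it.

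**Conclusion.** The point holds in a limited form. If IV+PO is used as Section 1.0 says, opioid use is understated in the epidural arm only. An epidural advantage in either epidural-versus-paravertebral comparison then cannot be reported as a lower total opioid requirement. The catheter versus single-shot comparison is sound in this respect.

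This rests on Section 1.0 governing the route-free wording of Sections 4.0 and 7.0, and on epidural hydromorphone counting towards total opioid with some non-negative weight. The direction follows from the documents; the magnitude does not.

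The weight is minor to moderate. Opioid use is a secondary outcome and appears in neither stated hypothesis, and the primary VAS analysis is unaffected. It should be corrected before analysis because the correction is cheap and the likely misreading favours one arm. The missing hypotension outcome is a separate and smaller gap.

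**What to change.** **Label and unit.** In Sections 1.0, 4.0 and 7.0, call the IV+PO endpoint *supplemental systemic opioid* and express it in one stated equivalent unit with its conversion source. State the clock start, and whether pre-block and intraoperative opioid count.

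**Total opioid.** Record epidural hydromorphone in mg for the epidural arm. Prespecify a secondary analysis of IV + PO + epidural opioid for the two epidural comparisons, over a sourced range of k that starts at zero and whose upper end is fixed before analysis. The zero-difference k may be added, but only where the epidural arm's IV+PO use is lower. It still depends on the chosen IV/PO conversion, and it applies to means on the original scale, not to the transformed or nonparametric analyses that Section 7.0 allows.

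**Claim.** State that IV+PO alone will not support a claim of lower total opioid requirement for the epidural arm. If infused volumes cannot be retrieved, report IV+PO under its supplemental label only and say that total opioid is not estimable in that arm.

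**Hypotension.** Add it as a descriptive outcome from routinely charted blood pressure, with one definition and time window for all arms, reported by randomized arm with 95% confidence intervals.

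**Cost.** The change is wording in three sections plus data abstraction. Treatment, sample size and primary analysis stay as they are. It assumes that infused volumes and blood pressures can be retrieved, which the documents do not describe; the relabelling works even if volumes cannot. The downsides are the extra abstraction, an uncertain epidural conversion, and a less favourable opioid figure for the epidural arm.

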7.0 Statistical Considerations

Primary outcome: VAS score at 24 and 48 hours

Primary Research Hypothesis: Thoracic epidural and Ultrasound guided paravertebral block with continuous catheter will provide lower pain scores compared to single shot paravertebral block.

Secondary outcomes: Opioid usage after 1, 24, 48 and 72 hours. Pain scores using VAS at rest and on movement at 1, 24, 48 and 72 hours. Patient satisfaction scores at 24 and 48 hours. Nausea scores at 1, 24, 48 and 72 hours. Sedation scores at 1, 24, 48 and 72 hours. Time to first bowel movement, incidence of urinary retention, and incidence of respiratory depression will be recorded as well.

Secondary Research Hypotheses: Thoracic epidural anesthesia and Ultrasound guided paravertebral catheter will show improved pain control, improved patient satisfaction scores, and decreased nausea and sedation scores compared to single shot paravertebral.

Statistical analysis will be performed using a standard statistical program (SAS or SPSS). All data will be summarized (means, standard deviations, standard errors, and ranges for continuous variables; frequencies and percentages for categorical variables) by group. Demographic data will be compared between the four groups using ANOVA or chi-square tests as appropriate. The primary outcome, VAS at 24 and 48 hours, will be compared between the groups using repeated measures ANOVA; the model will include fixed effects for group, time, and the group by time interaction and random effects to allow correlations between the two times and different variances for the two times. Pain and satisfaction scores and opioid usage over time will be analyzed using repeated measures ANOVA. Nausea and sedation scores will be compared between groups at each time point using Mantel-Haenszel chi-square tests for ordered categorical data. Distributions of the continuous variables will be examined, and a transformation of the data (e.g. natural logarithm) or nonparametric tests will be used as necessary. A 5% significance level will be used for all comparisons.

Based on prior studies, the coefficient of variation for the VAS score at 24 and 48 hours is estimated to be 0.70. With a sample size of 40 per group the study will be able to detect a 60% decrease in VAS score between any two groups, assuming two-sided tests each conducted at a 5% significance level.

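### Cheap precision gain for a secondary endpoint: the opioid-usage model names neither the opioid-naive/tolerant stratum nor the pre-admission opioid dose

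*Combined protocol and SAP*

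**What the plan says.** - **Aim.** The Rationale and Specific Aims (Section 1.0) list "2. Decreased opioid requirements".
- **Endpoint.** The same section says "The secondary endpoint includes intravenous opioid consumption and opioid side effects", and the next sentence says "The IV and PO opioid doses will be quantified at 1, 24, 48, and 72 hours". Section 7.0 has only "Secondary outcomes: Opioid usage after 1, 24, 48 and 72 hours". It gives no route, no common unit and no rule for opioid taken before admission.
- **Population.** Section 2.0 excludes recent substance abuse but not prescribed long-term opioid use. Section 3.0 says "Randomization will be stratified by prior opioid experience", naive or tolerant, and "Separate randomization lists will be used for the two strata".
- **Routes after surgery.** Under Section 4.0 every patient has a hydromorphone PCA, and oral oxycodone as needed is described as usual care from the first postoperative day.
- **Analysis.** Section 7.0: "Pain and satisfaction scores and opioid usage over time will be analyzed using repeated measures ANOVA". The only model terms spelled out are those for the primary outcome: group, time and their interaction. A transformation or a nonparametric test is allowed if the distributions call for it.

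Nowhere is the pre-admission opioid dose recorded, subtracted or used as a covariate.

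**The concern.** A tolerant patient's postoperative opioid total has two parts: the need created by surgery, which a block may reduce, and the need the patient brought along, which a block is not expected to change. The second part may appear as oral opioid or be replaced through the PCA, so it can enter the total whichever route the endpoint counts.

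If the model has no term for it, this part counts as unexplained variation between patients. A stratum term removes the average gap between naive and tolerant patients. It leaves the spread of home doses among the tolerant ones. At stake is the power to show an opioid-sparing effect of the catheter techniques over the single-shot block. The primary VAS outcome is not affected.

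**Working it through.** **1. The plan's own figure.** There is none for opioid usage. The only power statement concerns VAS: 40 per group, coefficient of variation (CV) 0.70, a 60% decrease, two-sided 5%. As a check, 0.60 / (0.70 × √(2/40)) = 0.60 / 0.1565 = 3.83, and 3.83 − 1.96 = 1.87, which is about 97% power. This says nothing about the opioid endpoint.

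**2. Inputs.** From the documents: 40 per arm and two-sided 5%. All else is assumed:
- 24-hour need from surgery: mean 40, SD 28 mg oral morphine equivalent (CV 0.70 borrowed from VAS), lognormal.
- Block effect: 35% less need, so a difference of 0.35 × 40 = 14 mg.
- Tolerant share: 20%. Home dose in that group: mean 60, SD 50 mg/day, lognormal, added in full to the total.

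**3. Raw-scale arithmetic, one time point, two arms.**
- Variance of need: 28² = 784 in one arm and (0.65 × 28)² = 331 in the other; sum 1,115.
- Home-dose variance per arm, within the tolerant group: 0.20 × 50² = 500.
- Home-dose variance per arm, between strata: 0.20 × 0.80 × 60² = 576.

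| Model | Standard error (mg) | 14 / SE | Approximate power |
|---|---|---|---|
| No adjustment | √((1,115 + 2 × 1,076)/40) = 9.0 | 1.55 | 34% |
| Stratum | √((1,115 + 2 × 500)/40) = 7.3 | 1.93 | 49% |
| Stratum + home dose | √(1,115/40) = 5.3 | 2.65 | 76% |

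**4. Simulation of the same setting.** This allows for skewness and adds the log-scale analysis that Section 7.0 permits. On the log scale home dose entered as log(dose + 1), because naive patients have dose 0.

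| Model | Raw scale | Log scale |
|---|---|---|
| No adjustment | about 35% | 61% (Mann-Whitney also 61%) |
| Stratum | 54% | 78% |
| Stratum + home dose | 78% | 82% |

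The simulated raw-scale standard errors are 8.9, 7.0 and 5.2 mg, close to the hand calculation.

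**5. Range.** Over 10–30% tolerant and mean home dose 45–90 mg/day:

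| Model | Raw scale | Log scale |
|---|---|---|
| No adjustment | 12–60% | 36–77% |
| Stratum | 33–70% | 70–82% |
| Stratum + home dose | 76–79% | 78–84% |

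At 5% tolerant and 45 mg/day, log-scale power goes only from about 80% to 84%.

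**6. Bias or precision?** With no block effect and strata balanced across arms, the mean arm difference is about zero. The unadjusted raw-scale model estimates a standard error of √((1,568 + 2 × 1,076)/40) = 9.6 mg. The true one, given balanced strata, is √((1,568 + 2 × 500)/40) = 8.0 mg. The critical value 1.96 then acts like 1.96 × 9.6/8.0 ≈ 2.36, a type I error of about 2%. The unadjusted test is conservative, not biased.

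**The case against.** The case against acting is substantial, and much of it stands.

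- **The plan already allows a remedy for skewed data.** A log or rank analysis limits the influence of a few high users. In the main setting it lifts unadjusted power from about 35% to 61%. Once the log scale and the stratum are both used, home dose adds only about 4 points (78% to 82%). This stands, and it means most of the log-scale gain comes from the stratum term. But the clause is conditional, and no stratum term is named, so neither safeguard is assured.
- **The gain from home dose depends on the additive assumption and accurate recall.** If recorded home dose differs from opioid actually taken by a multiplicative error with CV 0.5 to 1.0, raw-scale power with the covariate falls from 78% to about 59–68%. If tolerance scales need proportionally instead, raw-scale power is about 50% unadjusted and 70% with the covariate. This stands too: the benefit shrinks but does not disappear.
- **The documents make some allowance for tolerance.** They do, at the design stage. Separate lists balance the number of tolerant patients across arms, though not their doses, and randomization deals with the doses on average. A reader might infer that home opioid biases the arm comparison. It does not.
- **The endpoint may not count every dose.** A reader might take the quoted sentence to mean that all oral home opioid is counted. The sentence before it names intravenous consumption only, Section 7.0 says just opioid usage, and continued home opioid is never mentioned. The concern survives under either reading, because need replaced through the PCA is intravenous.

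**Conclusion.** This is a worthwhile, inexpensive improvement to one secondary endpoint, not an error that invalidates the analysis. Tolerant patients are enrolled and stratified, yet the opioid model names neither the stratum nor the home dose, so prior opioid need can cost power for the opioid-requirements aim.

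In the main setting, stratum plus home dose raises power from about 35% to 78% on the raw scale and from 61% to 82% on the log scale. With few tolerant patients on modest doses, the gain is close to nothing. These figures rest on an assumed tolerant share, home dose, postoperative need and effect, on a CV borrowed from VAS, and on home opioid adding fully to the total.

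It is tempting to go further and say that maintenance opioid swamps the block effect, or that the low raw-scale figures are the power of the plan. The documents support neither. They give no opioid figures, and the plan does not commit to a raw-scale analysis.

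**What to change.** 1. At consent, record each patient's pre-admission daily opioid dose in morphine equivalents, with 0 for naive patients. An opioid history is already needed to choose the randomization list. The field should be collected prospectively, because Sections 8.0 and 9.0 have identifiers destroyed at study end, after which it may not be recoverable.
2. Add to Section 7.0:

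> Opioid usage (IV and PO, in morphine equivalents, log-transformed if skewed) will be analyzed with group, time, group by time, the randomization stratum and pre-admission daily opioid dose (on the same scale as the outcome) as covariates.

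3. Make the endpoint sentences in Section 1.0 agree with this on routes, and state how zeros are handled on the log scale (for example, log(dose + 1)).

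**Cost:** one baseline field, two degrees of freedom, and a smaller gain if home dose is recalled with error. No extra patients, visits or procedures are needed, and clinical care is unchanged.
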